## Specific Aims and Hypotheses

### Aim 1.

The principle aim of our proposed clinical trial is whether an enhanced *mHealth care management model* with connected health technology used in partnership with the healthcare system team, an older person with heart failure (HF), and their caregiver are more effective than a *provider directed management model* using non-connected home equipment kits. Self-care of HF, quality of life and quality care are represented by multiple outcome measures that are important to patients, caregivers and healthcare (HC) systems. Specifically,

**Aim 1a. Patient-centered outcome measures:** We hypothesize that the mHealth model will increase measures from baseline to 3- and 6-month for the primary outcome of self-care management of HF compared to the provider-directed model. Further, we hypothesize that the mHealth model will increase measures from baseline to 3- and 6-month for secondary outcomes of Self-efficacy to manage symptoms, medications, & treatments; self-care confidence; physical function, sleep, social roles, (Promis 43v2.1 Health profile); heart failure knowledge; satisfaction with care; quality of life; informational support and equipment usability (3 and 6 months), while decreasing health distress, anxiety, depression, fatigue, and pain compared to the provider-directed model.

**Aim 1b. Caregiver outcome measures:** We hypothesize that the mHealth model will reduce caregiver burden, while increasing caregiver health compared to the provider-directed model from baseline to 6-months.

**Aim 1c. Health system outcome measures:** We hypothesize that the mHealth model will reduce hospital admissions, 1-month readmissions, emergency department

Study Title: Innovative Care of Older Adults with Chronic Heart Failure (I-COACH): A Comparative Effectiveness Clinical Trial  
PI (researcher): [name], RD  
Institution: University of Arkansas for Medical Sciences  
Funding: PCORI Grant

visits, and 6-month mortality of HF participants while increasing satisfaction with care, compared to the provider-directed model.

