Participants will be randomized then they will complete baseline measures (self-reported survey measures, see Table 1.). Because all participants & caregivers will participate in the same recruitment procedures, measure timelines, and will receive monitoring equipment, participants will be blinded to their assigned group and will not be informed of which is the active intervention group. Both groups will receive standard education provided by the hospital and clinic providers, in addition the study staff will emphasize portions of the standard education provided regarding *emergency situations that require immediate action from the patient and/or caregiver such as; hypertension crisis, stroke signs and symptoms, and signs and symptoms of heart attack.*

**The provider-directed management model** is the current standard of care in the treatment of patients with HF including guideline-based HF care and a fee-for-service payment model in which the number of services and procedures that are provided are billed. Patients are typically scheduled for provider visits at a periodic interval rather than on patient needs, preferences, or circumstances. Care delivery is based on convenience of provider and sometimes on priority-based queues, that is If patients are having problems, they typically call the providers office or set up an appointment to visit the clinic weekdays and get priority scheduled. If problems occur at a different time, they frequently go to the emergency department (ED) at a local hospital or UAMS.

Caregiver burden is substantial in this model considering the patients' problem solving, care, and transportation needs. Our previous research confirmed both the traditional call/wait approach and ED alternative as usual means of provider communications. However, in this study, we are supplementing standard care by providing and training each patient in the use of an analog kit: (not internet connected) weight scale, blood pressure cuff, pulse oximeter, and a Log for recording their vital sign measures. Patients will be trained on the equipment and told to obtain a reading of weight, BP, and POx saturation every morning when they arise. Participants will make appointments, receive consultations, case-management, and resolve problems through in-person appointments or telephone communications as usually scheduled during the 6-month study follow-up.

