PI (researcher): [name], RD  
Institution: University of Arkansas for Medical Sciences  
Funding: PCORI Grant

At that time, the participant's treatment plan may be altered by the provider to include increased vital sign tele-monitoring for that day, a change in medications, a video telemedicine home or in person office visit, or instructions to report to the emergency department for immediate evaluation and treatment if needed. The study team will not interfere with medical treatment and will not determine medical treatment. They will instruct the participant to follow prescribed protocols from their provider.

A "red light" is considered severe symptoms and/or critically abnormal vital signs. These patients are instructed at enrollment in the study *about emergencies that require immediate action (call 911 or go to the local emergency department) without waiting for a call from the call center, such as hypertension crisis, stroke signs and symptoms, and signs and symptoms of a heart attack.*

The call center will follow up on red alerts to make sure the participant followed standard education previously provided regarding emergencies and reeducate them and their caregiver as needed. As with all triage calls, this will be documented in the medical record.

If a yellow, or orange light occurs, and the participant does not answer the phone, the caregiver will be called. The caregiver will be instructed to make contact with the participant to return a call to the call center for instructions. If participant and caregiver are not available, a message will be left about the readings with instructions to telephone the call center number as soon as possible. A second call to the home and caregiver will be done this day if a return call is not received and same protocol will be followed as above. If no answer and no return call, this procedure will be followed per call center triage protocol.

mHealth participants will be told they can contact the call center RN for problems or concerns using the tablet or telephone and these will be triaged by RN call-center per protocol. Daily vital sign measures, recommendations, and responses will be transmitted, provider visits counted, tabulated and saved for analyses.

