### **Language**

Instruments will be provided for English and Spanish-speaking patients, may be read to the participants if desired, and will be installed with large print and/or an easy-to-use format loaded on the tablet device. Outcome data/measures for the provider and hospital system will be obtained from the electronic medical record and hospital computer database within 30 days after the 6-month follow-up measures have been completed.

Study Title: Innovative Care of Older Adults with Chronic Heart Failure (I-COACH): A Comparative Effectiveness Clinical Trial  
 PI (researcher): [name], RD  
 Institution: University of Arkansas for Medical Sciences  
 Funding: PCORI Grant

**Table 1. Specific Aim Addressed, Measure, Outcome Type, Purpose of Measure, Administration Interval & Estimated Participant Completion Time**

SP. AIM	Measure	Outcomes	Purpose of Measure	Base line	3 mth	6 mth	Completion Time
PATIENT CENTERED OUTCOME MEASURES							
1a	Self-Care of HF Index v7.2	Primary Outcome:	Assess self-care management, symptom perception & maintenance skills	X	X	X	8 min.
3	Self-Care Confidence 	Hypothesized Mediator:	Assess confidence in ability to care for self	X	X	X	3-5 min.
3	Promis® Self-Efficacy to Manage Symptoms 	Hypothesized Mediator:	Assess ability to manage symptoms for chronic conditions	X	X	X	15-20 min.
3	Promis® Self-Efficacy to Manage Medications & Treatments 	Hypothesized Mediator:	Assess ability to manage medication & treatments for chronic conditions	X	X	X	20 min.
3	Dutch HF Knowledge Scale 	Hypothesized Mediator	Assess Knowledge of HF	X	X	X	5 min
1a & 2	Promis® 43v2.1 Health profile 	Secondary Outcome Patient Characteristics	Assess physical function, anxiety, depression, fatigue, sleep, social roles, and pain	X	X	X	10-20 min.
1a	Health Distress 	Secondary Outcome Patient Characteristics	Assess psychological impact/health distress	X	X	X	1-3 min
1a	Promis® Informational Support v 2.0 6a 	Secondary Outcome	Assess perceived availability of helpful information or advice	X	X	X	2-4 min.
1a	System Usability Scale 	Secondary Outcome	Ease of using the technology		X	X	3-5 min.

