2	St. Louis University Mental Status (SLUMS) Examination 	Secondary Outcome: Patient Characteristic	Cognitive assessment (OBJECTIVE MEASURE)	X			10 min.
2	Patient Demographics (self-report & medical record review)	Secondary Outcome: Patient Characteristics:	Education, income, rurality, HF severity, years diagnosed, caregiver location, etc	X			5 min.
1a	Minnesota Living with HF (MLHFQ) 	Secondary & Long-Term Outcome	Assesses Quality of Life	X		X	5-10 min.
2	Newest Vital Sign 	Secondary Outcome: Patient Characteristics	Screens for Health Literacy	X			5 min.
CAREGIVER CENTERED OUTCOME MEASURES							
1b	Caregiver Burden 	Secondary Outcome	Assess caregiver perception of burden	X		X	30 min.
1b	Optum®SF-36® v2 Health Survey 	Secondary Outcome	Health domains- Functional Psych. Health & Well-being	X		X	5-10 min
PROVIDER & HEALTH SYSTEM MEASURES							
1c	Satisfaction with Care 	Secondary Outcome	Patient assesses satisfaction with care	X	X	X	1-3 min
1c & 2	Hospital, Emergency Visits, Provider Visits, Mortality	Secondary Outcome	Counts from Medical Record	X	X	X	N/A

Study Title: Innovative Care of Older Adults with Chronic Heart Failure (I-COACH): A Comparative Effectiveness Clinical Trial  
PI (researcher): [name], RD  
Institution: University of Arkansas for Medical Sciences  
Funding: PCORI Grant

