### **Inclusion Criteria HF Participants**

- Adults aged > 55 years with HF (documented in medical record).
- Has capacity to understand informed consent.
- Able to stand (briefly) without assistance.
- Has a designated caregiver.
- Agrees to be followed (treated) by UAMS physician/provider for 6 months after discharge.
- Community dwelling

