## Risks and Benefits

A risk to study participants is the potential for loss of confidentiality of study data. Measures to protect the confidentiality of study data will be implemented as described in the Data Handling and Recordkeeping section below. Other risks to participants in this study are minimal. We will minimize risks to the participants by using procedures already being performed with the subjects for diagnostic or treatment purposes, and we will only monitor the number of provider and hospital visits via the medical record. The medical management of the HF patients will not be changed or dictated in any way by this proposed research; only the mode of delivery, and only when applicable. If the participant needs diagnostic testing or an in-person appointment as determined by the provider, we will not dissuade or intervene in any way.

All participants will receive standard education provided by the hospital and clinic providers, in addition the study staff will emphasize portions of the standard education provided regarding emergency situations that require immediate action from the patient and/or caregiver such as; hypertensive crisis, stroke signs and symptoms, and signs and symptoms of heart attack. Participants and caregivers will be instructed to take *immediate action by calling 911 or going to the local emergency department without waiting for a call from the call center.*

We have a 24-hour RN call center that mHealth participants may contact if questions or problems, or they can contact their providers as they have in the past, using standardly developed procedures, such as calling the provider's office number or the "on-call" number if after hours. The call-center has been in existence for >10 years and has highly skilled RNs that are accustomed to handling issues/problems. Participants in the provider-based model will continue with standard access to their providers.

There will be no direct benefits to the study participants; however, knowledge gained from the study could potentially benefit patients in the future.

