Secondary Outcomes, including other patient centered, caregiver, and health system outcomes, will similarly be modeled using an ANCOVA approach. Hospital admissions and adverse events will be analyzed as proportion with unplanned admissions in the next 6 months and event rates using logistic models and models based on Poisson calculations or Negative Binomial to handle potential over-dispersion issues, and mortality and time to first unplanned hospitalization will be compared using survival methods such as log-rank tests and Cox proportional hazards models.

Evaluating heterogeneity of the treatment effect is a key consideration for Aim 2 since we want to identify which patients benefit most. The objective of the HTE analyses is evaluate whether the interventions produce differential benefits for subsets of participants. This will be investigated by including an interaction between baseline factors and intervention group (i.e., race x group) to the model above, and comparisons made using contrasts (model-based t-tests). The analytical approach taken is known as moderator analysis. Baseline factors include the demographic information as well as others measures, such as baseline self-care management score, age, race, rurality, gender, education, time since initial HF diagnosis, HF severity, depression, self-care confidence, etc. Factors with small subgroups ( $<20\%$  of the sample size) will not be investigated. If the arm x time interaction is significant, we will include 3-way interactions to investigate if the intervention effect differs by subgroup at each time point. When there is not a significant interaction with time, we will investigate how the arm effect differs for subgroups averaged across time. The proposed measures will be considered moderators if it meets the eligibility and analytic criteria described by Wang & Ware (2013). Using the model mentioned above, we will also analyze data as a binary endpoint (adequacy of self-care  $>70$  vs.  $<70$ ) in a repeated measures logistic model; with this approach we can also give the probability of achieving adequacy of self-care for various subgroups in addition to odds ratios.

Study Title: Innovative Care of Older Adults with Chronic Heart Failure (I-COACH): A

Comparative Effectiveness Clinical Trial

PI (researcher): [name], RD

Institution: University of Arkansas for Medical Sciences

Funding: PCORI Grant

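### Aim 1c admissions and emergency visits are counted from the medical record, but the plan foresees local emergency care and does not say whether the record shows it

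*Combined protocol and SAP*

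**What the plan says.** **Outcomes.** Aim 1c states: "We hypothesize that the mHealth model will reduce hospital admissions, 1-month readmissions, emergency department" visits, together with 6-month mortality. The Data Analysis section says: "Hospital admissions and adverse events will be analyzed as proportion with unplanned admissions in the next 6 months and event rates using logistic models", adds Poisson or negative binomial models, and compares time to first unplanned hospitalization by survival methods.

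**Source.** The last row of Table 1 gives "Counts from Medical Record" for hospital, emergency and provider visits. The Language section says that provider and hospital-system outcome data "will be obtained from the electronic medical record and hospital computer database within 30 days after the 6-month follow-up measures" are complete.

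**Where emergency care is sought.** The description of the provider-directed model says of patients with problems outside weekday clinic access that "they frequently go to the emergency department (ED) at a local hospital"; the sentence then names UAMS as the alternative. The red-light text for the mHealth arm tells patients to "call 911 or go to the local emergency department". The Risks and Benefits section gives all participants and caregivers the same direction: "calling 911 or going to the local emergency department without waiting for a call from the call center".

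**Partial mitigation.** An inclusion criterion reads: "Agrees to be followed (treated) by UAMS physician/provider for 6 months after discharge".

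**Provider visits.** The provider-directed description takes these from the electronic record plus self-report by the patient. The mHealth description says that they are counted but names no source. Table 1, the Language section and Risks and Benefits name the record or database only.

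**The concern.** The plan expects some emergency care outside UAMS, yet the only stated source for admissions and emergency visits is the record and the hospital's database. If these do not show encounters elsewhere, outside emergency visits, admissions and 1-month readmissions are scored as not having happened. Such an event is not flagged as missing, so the planned multiple imputation cannot recover it. The proportions, the event rates and the time to first unplanned hospitalization would all inherit the error.

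If capture is incomplete but equal in both arms, the risk or rate ratio is roughly preserved. The odds ratio from the logistic model moves toward 1, and events, absolute differences and power are lost. If capture differs by arm, the comparison is biased. Equal capture cannot simply be assumed: mHealth triage calls are written into the medical record, while nobody is alerted to readings in the provider-directed arm. The documents do not settle whether this produces a difference, or in which direction.

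Provider visits are a smaller, separate matter. They are in Table 1 but are not a hypothesized Aim 1c outcome. If self-report supplements the record in one arm only, the two counts are not comparable.

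**Working it through.** **Document check.**

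| Item | Stated source | Other facilities covered? |
|---|---|---|
| Admissions, emergency visits | Record (Table 1); record and hospital database (Language) | Not stated |
| Provider visits, provider-directed text | Record and self-report | Self-report could cover them; not stated |
| Provider visits, mHealth text | None named | Not stated |
| Provider visits, Table 1, Language, Risks and Benefits | Record or database | Not stated |

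Self-report appears once, for provider visits only, so it does not fill the gap for admissions or emergency visits. The inclusion criterion concerns who follows the patient, not where emergency or inpatient care is received. No section names claims data, an information exchange or requests for outside records.

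**Illustration of size.** The documents give no event rate, capture rate or power for these outcomes, so there is no figure to reproduce. From the documents: 400 patients. Assumed: 1:1 allocation (200 per arm), 40% vs 28% with at least one event, two-sided alpha 0.05, and equal capture *c* in both arms.

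Power = Φ[(d − 1.96·SE₀)/SE₁], where d = p₁ − p₂, SE₀ = √(2p̄(1 − p̄)/200) and SE₁ = √([p₁(1 − p₁) + p₂(1 − p₂)]/200).

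At full capture d = 0.12, p̄ = 0.34, SE₀ = 0.0474 and SE₁ = 0.0470. Power = Φ[(0.12 − 1.96 × 0.0474)/0.0470] = Φ(0.58) = 0.718.

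Two models of capture bracket the loss:

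- Per patient: recorded p = c × p.
- Per event, with Poisson events: means −ln(1 − 0.40) = 0.511 and −ln(1 − 0.28) = 0.329; recorded p = 1 − exp(−c × mean).

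| Capture | Model | Recorded p | Difference (points) | Risk ratio | Odds ratio | Power |
|---|---|---|---|---|---|---|
| 100% | – | 0.400 vs 0.280 | 12.0 | 0.700 | 0.583 | 0.718 |
| 85% | per patient | 0.340 vs 0.238 | 10.2 | 0.700 | 0.606 | 0.615 |
| 85% | per event | 0.352 vs 0.244 | 10.9 | 0.692 | 0.592 | 0.662 |
| 70% | per patient | 0.280 vs 0.196 | 8.4 | 0.700 | 0.627 | 0.505 |
| 70% | per event | 0.301 vs 0.205 | 9.5 | 0.683 | 0.601 | 0.591 |

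Differences are taken from unrounded values. In the per-event model the rate ratio is 0.643 at every capture level. Simulation (200,000 replicates) gave power of 0.721 at full capture, 0.617 and 0.507 per patient at 85% and 70%, and 0.663 and 0.594 per event.

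**Unequal capture, also assumed.** Per patient, the recorded risk ratio is the true ratio times (mHealth capture/control capture). With a true ratio of 0.70, capture of 70% in control and 90% in mHealth gives 0.70 × 0.90/0.70 = 0.90; the reverse gives 0.70 × 0.70/0.90 = 0.54. With no true effect (40% in both arms), capture of 70% in control and 90% in mHealth gives 28% vs 36%, a ratio of 1.29 and about a 40% chance of a significant result. Nothing in the documents shows capture this unequal.

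**The case against.** The first part is an argument from silence. Nothing says that the record omits outside encounters, and the database is not expressly limited to UAMS care. A Data Management Plan is still to be written and may deal with the point. The sentence about local hospitals describes typical care under the provider-directed model and names UAMS too; the emergency instructions are generic, and for some patients the local department may be UAMS. Retrieval from the record is specified identically in both arms, the rate ratio survives equal under-capture, and every magnitude is assumed. The provider-visit mismatch is partly inferred from where one sentence sits. Self-report brings recall error and attrition, and the completion times in Table 1 already add up to about 73–103 minutes for patients at 6 months.

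Much of this is right and limits the claim: no missed events, bias or direction is shown, and the illustration is not evidence from the trial. What it does not remove is the gap. The plan names local hospitals as a destination distinct from UAMS, sends participants to local departments, and states a source whose reach it does not define. A data plan yet to be written does not change that source. The added burden is real but small, and the record-only count stays available.

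**Conclusion.** The point holds. The stated source may or may not show admissions and emergency visits at other facilities, and the plan offers no alternative if it does not. Under the assumed rates and equal capture, 70% capture would cut power from 72% to 51–59% and the recorded difference from 12.0 to 8.4–9.5 points, while moving the odds ratio only from 0.583 to 0.601–0.627. These figures depend on assumed event rates, capture and 1:1 allocation. Bias between arms is possible but not shown. The inconsistency on provider visits is in the text; that the arms would actually use different sources is a possibility. The primary outcome is unaffected, so this is something the team should change rather than a threat to the trial's main conclusion. It matters because these outcomes carry the utilization part of Aim 1c.

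**What to change.** 1. State whether the record and hospital database show encounters at other facilities.
2. At the existing 3- and 6-month contacts, ask all patients in both arms the same questions about admissions, emergency visits and provider visits at any facility since the last contact, with date and facility.
3. Report by arm both the record-only count and the combined any-facility count, de-duplicated by date and facility. Prespecify which is the main analysis and which the sensitivity analysis.
4. Report completion of the self-report questions by arm.
5. Name one source for provider visits, identical in both arms, and reconcile the two arm descriptions, the Language section, Table 1 and Risks and Benefits.

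The cost is a few questions at contacts already scheduled, plus protocol wording. The downsides are recall error, and missing self-report for patients who are lost or die before a contact; the plan anticipates up to 10% deaths by six months and possible differential dropout. Either could make combined capture unequal. Assumed example: record capture 70%, recall 80%, 90% of patients reached in one arm and 80% in the other, no false reports. Combined capture is 0.70 + 0.30 × 0.90 × 0.80 = 0.916 and 0.70 + 0.30 × 0.80 × 0.80 = 0.892. The rate ratio shifts by a factor of 0.974 or 1.027, depending on the arm, which is about 3%. The record-only analysis needs no patient contact and helps to judge this.
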